4. STUDY DESIGN

4.1. DESIGN / STUDY TYPE

This is a pragmatic cluster randomised controlled trial. The unit of randomisation is the team. The teams are four of the five Adult Community Mental Health 'Core' Teams in SLHD (Table 1). Randomisation will be stratified by sector (Eastern and Western): One team from each sector will be randomised to the intervention group, the other team will be allocated to the comparison group. The comparison group Teams will receive the intervention after the 3-month data collection is complete.

As there are only two teams per sector in the study, randomisation will be done by a person independent from the study by flipping a coin.

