4.2. EXPECTED PARTICIPANT NUMBERS

We aim to recruit 500 consumers and expect 400 to remain in the study at 3-month follow-up (20% loss to follow up). Power calculation: Assuming 20% change in the frequency and quality of primary and preventative care received by participants, a sample size of 91 per group is required to detect a change from 30 to 50% in primary outcomes based on $\alpha = 0.05$, $1-\beta = 0.8$. Assuming a design effect due to clustering of 2, a total sample of 360 is required (180 in each group).

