Secondary data from GP records, and SLHD eMR data (including hospitalisations, ED visits and ambulatory care records, associated costs, documentation audit report and metabolic report) as well as information from SLHD Targeted Activity & Reporting System (STARS) will be obtained and merged with the consumer survey data within the SLHD by AI [name]/AI [name]. GP records will be used to answer research questions 1 and 2 – quantitative analysis is described above. SLHD's patient data from the eMR (including hospitalisation, ED visits, ambulatory data, documentation audit and metabolic monitoring) as well as information from STARS and cost information will be used to answer research questions 3 and 4. These analyses of the resulting combined and de-identified dataset are described below.

The merged SLHD administrative data (micro-level data) will be from a 6-month period post-intervention (May-October 2023, considering the intervention as having a shared care plan in Inca between May and June 2023) compared with the 6-month periods, a) pre-intervention (November 2022-April 2023) and b) in the previous year (May-October 2022, to check for seasonal effect). The data will be analysed as part of the healthcare cost component (in the larger health economic evaluation).

The healthcare usage (such as hospitalisations, ED visits, ambulatory care and GP care) data will firstly be grouped in a meaningful way e.g., for hospitalisations, summarised by ARDRGs, diagnoses and average length of stay. Costs will be summarised too e.g., for hospitalisation costs, these will be described in terms of main components such as 'Medical', 'Nursing' and 'Allied Health' costs occurring during admissions. We will calculate the total and mean utilisation of healthcare services and costs (and undertake further econometric analyses) for those in the SHAReD intervention, usual care, and combined (SHAReD and comparison) groups. These summary statistics (and later modelled estimates) will be included in the cost component of the economic evaluation.

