A within-trial economic evaluation of the SHAReD intervention compared to usual care will be conducted if effectiveness has been demonstrated. The mean costs and health effects/benefits will be used to generate the incremental cost for a one-unit improvement in the health effect of interest (e.g. an extra Quality Adjusted Life Year [QALY]) for the SHAReD group compared to the usual care group. We will assemble several ICERs such as the incremental cost for each care plan completed, the reduction in cases with cardiometabolic risk (and separate risk factors), unplanned hospital admissions avoided, and a gain in QALYs among the SHAReD group compared with the usual care group. The results of the evaluation will be used to determine the within-trial cost-effectiveness (and utility) of the SHAReD intervention i.e. whether it offered value for money.

The results will be shown graphically on a cost-effectiveness plane.³² Thus, the cost-effectiveness plane will show the differences in healthcare costs and health effects/benefits between the SHAReD intervention and usual care groups in two dimensions, with the healthcare costs plotted against health effects/benefits. We will use the bootstrap method, which is a re-sampling method used to estimate basic statistics on a population through sampling the dataset with replacement, to create 10,000 random samples and then use these samples to establish a statistical distribution for the costs and health effects/benefits (means and standard deviations) in the intervention and control groups, as well as to generate confidence intervals for the applicable ICER.³³ Various sensitivity

analyses will be undertaken. We will also generate a cost-effectiveness acceptability curve to summarise the impact of uncertainty on the results of the evaluation, expressed as the main ICER in relation to possible values of the cost-effectiveness threshold.³⁴ Values for thresholds will be determined by considering what is meaningful for the healthcare provider.

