Health related quality of life will be collected using the EuroQol five dimensions, 5 levels questionnaire (i.e. EQ5D5L), which is a reliable and validated utility-based and disease-generic quality of life measure used for medical decision-making in Australia and elsewhere. The cost-effectiveness study will use QALYs gained as one of the main health effects based on the EQ5D5L questionnaires administered at baseline, during, and at completion of the trial. Factors for changes in the quality of life (including the various domains, visual analogue score, overall score and QALYs) of study participants over time will also be explored using a range of econometric methods, such as difference in difference models, generalised linear mixed models (GLMMs) for repeated measures /panel data and other panel data methods.

The effects of the SHAReD intervention on employment and other activities undertaken by participants (and costed out) will be examined using summary statistics and logistic/probit models.

The economic evaluation will apply established principles and methods for undertaking cost-effectiveness (and cost-utility) analyses, consistent with the National Health and Medical Research Council's (NHMRC) economic evaluation guidelines.³⁵

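### The cost-effectiveness analysis is conditional on demonstrated effectiveness although objective 4 and hypothesis 4 are not, its bootstrap names no clustering, and its cost and EQ-5D periods are not aligned

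*Protocol*

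**What the plan says.** **Condition on running the analysis.** Protocol Section 8.2 (Costing component and the economic evaluation) states: "A within-trial economic evaluation of the SHAReD intervention compared to usual care will be conducted if effectiveness has been demonstrated". The synopsis (Statistical considerations) repeats this and makes the cost-utility analysis depend on a shown effect on quality of life. Research question 4 in Section 3 is worded conditionally. Objective 4 in the synopsis and hypothesis 4 in Section 2 ask about, or predict, cost-effectiveness with no condition.

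**Bootstrap.** Section 8.2 describes "sampling the dataset with replacement, to create 10,000 random samples". These samples give the distributions of costs and effects and serve "as well as to generate confidence intervals for the applicable ICER". No resampling unit is named, and neither team, care coordinator nor GP is mentioned there. Section 4.1 states: "The unit of randomisation is the team", with four teams: "One team from each sector will be randomised to the intervention group, the other team will be allocated to the comparison group". Section 4.2 uses a design effect of 2 for clustering, and the effectiveness models in Section 8.2 allow for nesting within care coordinators, teams and GPs.

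**Timing.** On costs, Section 8.2 says "The merged SLHD administrative data (micro-level data) will be from a 6-month period post-intervention", namely May to October 2023. QALYs are to be "based on the EQ5D5L questionnaires administered at baseline, during, and at completion of the trial". Table 6 (Section 6.2) and Section 9.2 schedule the consumer survey, which carries the EQ-5D, at baseline and at follow-up only.

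**The concern.** Value for money depends on incremental cost and incremental effect together. An intervention whose effect is uncertain can still be good value if it saves money, and hypothesis 4 predicts cost avoidance. A prior test of effect removes that case from the full analysis. When the test is passed, the effect estimates that go forward are on average too high, because those that fell low by chance have been filtered out.

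If the resampling treats consumers as independent, the ICER intervals and the acceptability curve will look more certain than four randomised teams can support.

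If costs and QALYs cover different periods, their ratio has no clear time horizon. If QALYs are planned around a measurement that is never taken, the area-under-the-curve calculation cannot be done as written.

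**Working it through.** **1. The condition, text against text**

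- Synopsis, objective 4: no condition.
- Section 2, hypothesis 4: no condition.
- Section 3, research question 4: conditional on effectiveness.
- Synopsis, Statistical considerations: cost-effectiveness conditional on effectiveness; cost-utility conditional on a quality-of-life effect.
- Section 8.2: within-trial evaluation conditional on effectiveness.

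These cannot all stand. Two economic outputs are unconditional: the cost-consequence analysis and the adjusted incremental cost models, both in Section 8.2. The first presents costs and outcomes in disaggregated form. Neither yields an ICER or an acceptability curve.

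**2. The plan's own sample size**

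Inputs from Section 4.2: 30% against 50%, alpha 0.05 (two-sided assumed), power 0.80, design effect 2.

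- n per group = (1.96 + 0.8416)² × (0.30 × 0.70 + 0.50 × 0.50) / 0.20² = 7.849 × 0.46 / 0.04 = 90.3, so 91. This matches the protocol.
- 91 × 2 groups × 2 = 364, against the stated 360; the difference is rounding.

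**3. Effect of leaving clustering out of the bootstrap**

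The protocol gives no design effect for costs or QALYs. As an assumption, apply the 2 that it states for the binary primary outcomes.

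- Ratio of standard errors = 1/√2 = 0.71. Correct intervals would be √2 = 1.41 times as wide.
- Coverage of a nominal 95% interval for a mean difference = 2Φ(1.96/√2) − 1 = 2Φ(1.386) − 1 = 0.834, about 83%.
- If the clustering is by team, with 400 retained over four teams (about 100 each), the implied intraclass correlation is (2 − 1)/(100 − 1) = 0.010. Simulating two teams of 100 per arm at that value, with consumers resampled singly, gave 82% coverage.

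The same formula for other assumed team-level correlations, with design effect 1 + 99 × ICC:

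| ICC (assumed) | Design effect | Coverage |
|---|---|---|
| 0.005 | 1.50 | 89% |
| 0.010 | 1.99 | 84% |
| 0.02 | 2.98 | 74% |
| 0.05 | 5.95 | 58% |

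Resampling whole teams is no cure. Drawing two teams with replacement from two gives only three distinct samples per arm, and simulated coverage was about 65–67% over these correlations. Resampling GPs or care coordinators within fixed teams leaves the between-team variance out.

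**4. Time points and windows**

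- Section 8.2 lists three EQ-5D occasions; Table 6 and Section 9.2 provide two. This contradiction needs no assumption.
- Administrative costs cover six months, May to October 2023.
- Table 2 puts recruitment in March to December 2022, and the synopsis places baseline as soon as possible after recruitment. Follow-up is three months after shared care or, without an appointment, three months after 30 June 2023, i.e. about the end of September 2023.
- For illustration, assume that baseline falls in the month of recruitment and follow-up on that fallback date. The EQ-5D interval is then about 9 months (from December 2022) to 18 months (from March 2022). Real dates may differ, and the protocol does not say how QALYs will be computed between surveys.

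**The case against.** **The resampling unit is not written.** Section 8.2 gives a textbook description of the bootstrap, and the unit could be fixed in an analysis plan not shown here. This stands as far as it goes: the text does not say that single consumers are resampled. It does say that the dataset is resampled, and rows are the natural reading. It adds nothing about clusters, although the effectiveness models in the same section do.

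**The design effect is borrowed.** It was stated for binary primary outcomes, and the coverage formula is for a mean difference, not for a ratio. Both limits are real, so 83% is conditional.

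**Much of objective 4 is answered anyway.** Costs and outcomes by group, and adjusted cost differences, are produced whatever the result. This also stands, for the descriptive part.

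**A stronger reading on the condition.** A reader might infer that the cost-effectiveness question would usually go unanswered. The protocol's figures do not support this. At its planned 80% power, a test of one primary outcome would fail about 20% of the time (1 − 0.80) if the assumed effect were real. A much higher figure would need a test on between-team degrees of freedom, which the protocol does not fix; it selects random effects after inspecting intraclass correlations. Nor does the protocol tie demonstrated effectiveness to one outcome.

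**A stronger reading on the horizons.** A reader might also infer a definite inflation of QALYs relative to costs. That would need survey dates and an interpolation method that are not given. Table 9 labels the EQ-5D score as covering the last six months, which suggests that matching periods may be intended.

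**Conclusion.** The point holds in three parts of different firmness.

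- **Condition on effectiveness: firm.** It is a stated rule that conflicts with objective 4 in the synopsis and with hypothesis 4. It puts a test of effect in place of a joint question about cost and effect. How often it would stop the analysis cannot be derived from the document.
- **Bootstrap: holds on the natural reading.** As described, it carries none of the clustering recognised elsewhere. If consumers are resampled singly and a design effect of 2 applies to costs and effects, the standard error is about 29% too small (1 − 0.71) and coverage is about 83% for a mean difference. The figure for the ICER itself was not computed.
- **Timing: part firm, part open.** The EQ-5D during the trial contradicts Table 6 and Section 9.2. The cost and QALY periods may differ, but the size of any mismatch depends on dates and a method that the protocol does not give.

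**What to change.** - Report incremental cost, incremental effect, net benefit and the acceptability curve whatever the effectiveness result, including for QALYs. Align the synopsis (Objectives and Statistical considerations), Section 2, Section 3 and Section 8.2 with this.
- Estimate costs and effects jointly with a model that carries the same clustering as the effectiveness model, for example a bivariate multilevel model or a two-stage bootstrap with shrinkage. Do not use a row-level or a plain team-level bootstrap. State that four teams limit any such method.
- State one common window for costs and QALYs, and how QALYs are calculated over it.
- Correct the EQ-5D sentence in Section 8.2 to the two scheduled time points.

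The cost is a little more analysis work and wider intervals. No new data collection is needed.

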

Statistical considerations
	
Sample size calculation Assuming 20% change, a sample size of 91 per group is required to detect a change from 30 to 50% in primary outcomes based on $\alpha = 0.05$, $1-\beta = 0.8$. Assuming a design effect due to clustering of 2, a total sample of 360 is required (180 in each group).
 
Analysis plan For analysis of differences between the intervention and usual care alternatives, linear or generalised multi-level mixed models will be estimated depending on the type of outcome in question. Intra-class correlations will be calculated to compare the amount of variance associated with design features as individual participants are nested within care coordinators who are nested within community mental health teams, and those same participants are also nested within GPs who may also be nested within medical centres, which will occur before selecting random effects for these models. As well as an analysis of completers, defined as those consumers, care coordinators and GP triads that complete an online shared care plan, an intention to treat (ITT) analysis will also be completed for this study. For the ITT analysis, those who have dropped out will be treated using a variety of sensitivity analyses. Further, baseline predictors and intervention features of both the SHAReD (e-shared care) and usual care situations will be added to multi-level models to identify effects of these characteristics on outcomes. Qualitative analyses (predominantly deductive but inductive coding will also be applied to detect new and emerging themes) will also be undertaken. All relevant costs such as implementation costs and healthcare usage [hospitalisations, GP care, specialists, allied health, and prescribed medication, and the multiple outcomes such as interactions with the health system, engagement, preventive tests undertaken, clinical measures and quality of life for participants in the intervention and usual care groups will be quantified, and tests of significance will be undertaken on these data. These results will be used in a cost-consequence analysis (CCA). A comprehensive within-trial cost-effectiveness study will also be conducted provided effectiveness has been demonstrated, with the main effects/benefits consisting of satisfactory completion of an online shared care plan, reduction in consumer cardiometabolic risk, and avoiding unplanned hospitalisations. A cost-utility evaluation will be conducted if effectiveness in relation to quality of life has been demonstrated, to provide a ranking of the alternatives (e-shared care, usual care) on the basis of the amount of resources (costs) used to gain an extra quality adjusted life year (QALY) by receiving the SHAReD intervention. All the necessary effects/benefits and costs (direct medical, consumer costs for medical care and any indirect costs) will be identified, counted and valued using established methods. A range of incremental cost-effectiveness ratios (ICERs) will be calculated such as the incremental cost for an extra QALY gained, cost for an unplanned hospitalisation that was avoided. Sensitivity analysis will be conducted and some results presentations graphically.

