2. HYPOTHESIS

1. After 3 months, the intervention will improve the frequency and quality of primary and preventive care received by study participants in intervention sites compared to participants in sites with usual care.
2. After 3 months, the intervention will better integrate care between mental health services and general practice compared with usual care.
3. After 3 months, the intervention will improve consumer health risks and service use compared with usual care.
4. After 3 months, the intervention will demonstrate cost-effectiveness compared to usual care (i.e. the situation without the intervention) and *cost avoidance* (i.e. there will be reduced costs in the intervention group).

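### The planned bootstrap intervals for several ICERs have no rule for negative ratios or mixed quadrants, although the plan expects lower cost with better outcome (minor)

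*Protocol*

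**What the plan says.** Protocol section 8.2, under the costing component and economic evaluation, describes a within-trial evaluation that "will be conducted if effectiveness has been demonstrated". It plans more than one ratio: "We will assemble several ICERs such as the incremental cost for each care plan completed", followed by ratios for cardiometabolic risk, unplanned admissions and QALYs. Uncertainty comes from a bootstrap "to create 10,000 random samples", which serves to describe the distributions of costs and effects "as well as to generate confidence intervals for the applicable ICER".

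Two displays accompany the interval. "The results will be shown graphically on a cost-effectiveness plane", and an acceptability curve is to summarise uncertainty over possible thresholds. No threshold value is given.

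The expected direction is in section 2. Hypothesis 3 states that "the intervention will improve consumer health risks and service use compared with usual care", and hypothesis 4 expects cost-effectiveness and cost avoidance, explained as "there will be reduced costs in the intervention group".

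The synopsis (Statistical considerations) adds a narrower condition for one ratio: "A cost-utility evaluation will be conducted if effectiveness in relation to quality of life has been demonstrated".

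The protocol says nothing about how a negative ICER, or replicates falling in different quadrants of the plane, will be handled. It does not mention net benefit.

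**The concern.** If the intervention saves money and improves outcome, incremental cost is negative and incremental effect is positive. The ratio is then negative, and two of its properties fail.

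- **Size carries no order.** A larger gain for the same saving moves the ratio towards zero, while a smaller gain makes it more negative.
- **Sign alone is ambiguous.** A result with higher cost and worse outcome also gives a negative ratio.

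A percentile interval sorts replicates by this quantity. Under the plan's own hypothesis its lower limit tends to come from the replicates with the smallest gains, so it is not the favourable end of the range. Section 8.2 uses these results to judge whether the intervention gave value for money, so a reader could take the two limits for a best and a worst case.

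This is more than a detail left open. The protocol names a statistic that behaves badly in the situation it predicts.

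**Working it through.** The protocol gives no expected cost difference, effect difference, standard error or threshold, so it has no figure of its own to reproduce. All magnitudes below are illustrative assumptions.

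**Formulas.** With dC the incremental cost, dE the incremental effect and L the threshold per unit of effect:

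- ICER = dC / dE
- Net monetary benefit, NMB = L × dE − dC

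**Step 1: ordering** (L = 50,000 assumed).

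| dC | dE | ICER | NMB |
|---|---|---|---|
| −1,500 | 0.02 | −75,000 | 1,000 + 1,500 = 2,500 |
| −1,500 | 0.04 | −37,500 | 2,000 + 1,500 = 3,500 |
| −2,000 | 0.02 | −100,000 | 1,000 + 2,000 = 3,000 |
| −2,000 | 0.01 | −200,000 | 500 + 2,000 = 2,500 |
| +2,000 | −0.02 | −100,000 | −1,000 − 2,000 = −3,000 |

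Rows 1 and 2: doubling the gain makes the ratio less negative, though NMB rises. Rows 3 and 4: the more negative ratio belongs to the poorer result. Rows 3 and 5: a dominant and a dominated result share one ICER. NMB orders all five correctly.

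**Step 2: when the upper limit can be read.** If dE > 0, ICER < L is the same event as NMB > 0, so an upper limit below L supports cost-effectiveness. If dE < 0, the inequality reverses and the equivalence fails. What matters is the share of replicates with dE ≤ 0.

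The table uses 10,000 draws of (dC, dE), independent and normal, with dC = −1,000 (SE 600), dE = 0.02 and L = 50,000. The SE of dE varies.

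| dE / SE | 95% interval, ICER | 95% interval, NMB | Share ICER < L | Share NMB > 0 |
|---|---|---|---|---|
| 4 | −143,185 to 7,802 | 751 to 3,267 | 0.9989 | 0.9989 |
| 2.8 | −197,187 to 10,794 | 621 to 3,356 | 0.9952 | 0.9973 |
| 1.96 | −337,718 to 60,268 | 426 to 3,522 | 0.9737 | 0.9935 |
| 1 | −521,871 to 484,885 | −330 to 4,300 | 0.8772 | 0.9545 |

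From the first row to the third, the ICER's lower limit falls from −143,185 to −337,718 while the lower NMB limit gets worse, from 751 to 426. A more negative limit here reflects a less certain effect, not a better result. At 1.96 SE the ICER's upper limit lies above the threshold although the NMB interval excludes zero. The last row can arise only for a ratio whose own effect has not been shown. The synopsis condition would exclude it for the QALY ratio.

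**Step 3: with the effectiveness condition applied.** Trials were simulated with 200 per arm (section 4.2 expects 400 of 500 at follow-up; 400 / 2 = 200). Assumed inputs were a mean 6-month cost of $5,000 (SD $8,000), a QALY SD of 0.10, a true saving of $1,500 and a true gain of 0.02 QALY. Only trials with a significant QALY gain were kept.

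- About 89% of replicates were dominant. The median ICER interval was about −$221,000 to +$4,900, and 57% of intervals spanned zero. These figures shift somewhat with the assumed cost SD in the intervention arm.
- On average about 0.6% of replicates had a non-positive effect (maximum 3.2%). An ICER upper limit below $50,000 agreed with an NMB lower limit above zero in 96.5% of trials.

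With the condition met on the ratio's own effect, the upper limit is mostly usable. The lower limit is not.

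**Step 4: is the condition tied to each ratio?** Section 8.2 asks only that effectiveness be demonstrated, then lists ratios on several effect measures. The synopsis names quality of life for the cost-utility analysis and no matching condition for the others. A ratio could therefore be computed on a measure with no demonstrated effect. Where the effect is clearly positive, as may be so for plan completion, a cost saving still gives a negative ratio that shrinks towards zero as more plans are completed.

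**The case against.** A reader might infer that the interval cannot be read at all, that it will be the headline statement of precision, or that it undermines the cost-avoidance claim. The documents do not support these readings.

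- **The effectiveness condition matters.** It keeps most replicates at dE > 0, and the upper limit then remains readable (Steps 2 and 3). An interval from negative to positive with positive effects just spans cost saving to cost increase, which is ordinary uncertainty. Very wide QALY intervals obtained without the condition describe an analysis the plan would not run.
- **Nothing makes the ICER interval the headline.** Section 8.2 gives the task of summarising uncertainty to the acceptability curve, and both curve and plane remain useful when costs fall.
- **Cost avoidance is analysed separately.** It has its own row in section 7, Table 9, and its own incremental cost models in section 8.2.
- **Dominance is not certain.** The cost side also carries training, technology and general practice time, so net cost could rise even if service use falls, and the ICER would then be ordinary.
- **A reporting rule could sit in an analysis plan not seen here.**

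All of this limits the size of the point. It does not remove it: the lower limit stays meaningless when costs fall, the condition is not tied to every ratio, and displays beside an interval do not correct it. The curve also has a loose end, because section 8.2 describes it in terms of the main ICER against thresholds. If it were computed as the share of ratios below the threshold, it would err once replicates cross zero effect (0.8772 against 0.9545 in the last row of Step 2).

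**Conclusion.** The point holds in a limited form and is minor. The protocol commits to bootstrap intervals for several ICERs, expects the quadrant where a negative ratio has no order, and gives no rule for that case. The lower limit would then not be a best case. The upper limit can be compared with a threshold only if nearly all replicates have a positive effect, which the plan's condition secures for the QALY ratio but not clearly for the others.

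The ordering failure is arithmetic and needs no assumption. Every interval and percentage shown rests on assumed costs, QALYs, standard errors and a $50,000 threshold, none of which is in the protocol. No primary or clinical effectiveness conclusion is affected, and the analysis is secondary and conditional.

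**What to change.** From the same 10,000 bootstrap samples:

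1. Report incremental cost, incremental effect and incremental net monetary benefit, each with a 95% interval, with net benefit shown over a stated range of thresholds.
2. Keep the plane, and define the acceptability curve as the share of replicates with positive net benefit at each threshold.
3. Give an ICER interval only when essentially all replicates lie in the quadrant of higher cost and better effect. Otherwise give none, and report 'dominant' or 'dominated' where that applies.
4. State whether effectiveness must be shown on each ICER's own effect measure before that ratio is calculated.

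This costs a few sentences of analysis-plan wording and a few lines of code, with no new data. The downside is slightly more reporting, with a curve over thresholds in place of one ratio interval.
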